## 5.2 Exclusion Criteria

1. Type 1 diabetes mellitus
2. Active chronic liver disease, alcoholic liver disease, Wilson's disease hemochromatosis, primary biliary cirrhosis, primary sclerosing cholangitis, genetic hemochromatosis, known or suspected hepatocellular carcinoma, history of or planned liver transplant for end-stage liver disease of any etiology
3. Documented history of advanced liver fibrosis
4. History of cirrhosis and/or hepatic decompensation including ascites, hepatic encephalopathy, or variceal bleeding
5. Uncontrolled hypertension (systolic > 160 or diastolic > 100 mm Hg)
6. History of acute kidney injury within 12 months of Screening
7. Active infection requiring systemic antiviral or antimicrobial therapy that will not be completed prior to Study Day 1
8. Subjects with a history of major bleed or high-risk of bleeding diathesis
9. Clinically-significant abnormalities in screening laboratory values that would render a subject unsuitable for inclusion, including the following:

- a. Positive test (including trace) for blood on urinalysis. In the event of a positive test, eligibility may be confirmed with urine microscopy showing  $\leq 5$  red blood cells per high power field
  - b. Urine protein/creatinine ratio (UPCR)  $\geq 0.25$  mg/mg. In the event of a UPCR above this threshold, eligibility may be confirmed by a quantitative total urine protein measurement of  $< 300$  mg/24-hr
  - c. Estimated GFR  $< 60$  mL/min/1.73 m^2 (as determined by the Chronic Kidney Disease-Epidemiological Collaboration (CKD-EPI) Equation)
  - d. Alanine aminotransferase (ALT) or aspartate aminotransferase (AST)  $> 2$  x ULN
  - e. Bilirubin  $> ULN$ , unless prior diagnosis and documentation of Gilbert's syndrome in which case total bilirubin must be  $\leq 3$  mg/dL
  - f. Alkaline phosphatase (ALP)  $> 1.5$  x ULN
  - g. Platelet count  $< LLN$
10. Known history of or positive test for human immunodeficiency virus (HIV), hepatitis C or chronic hepatitis B
  11. Uncontrolled hyper- or hypothyroidism. Subjects on dose stable replacement therapy for at least 3 months prior to Screening will be allowed
  12. History of clinically significant acute cardiac event within 6 months before Screening (includes stroke, transient ischemic attack, and coronary heart disease [angina pectoris, myocardial infarction, revascularization procedures])
  13. History of heart failure with NYHA greater than Class II

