A confirmed laboratory value is based on consecutive lab values within 7 days (no matter central lab data or local lab data). If consecutive value is the same or worse, then the initial value is confirmed. If the consecutive value is better, then the initial value is confirmed using consecutive value category. In essence, when the consecutive value is better, the initial value is not confirmed. If there is no retest within 7 days then the initial value is presumed confirmed. If there are multiple results on the same day (no matter from the same lab vendor or different lab vendors), then the worst value will be utilized in the analysis.

The following lab results will be graded per Guidance for Industry: Toxicity Grading Scale for Healthy Adult and Adolescent Volunteers Enrolled in Preventive Vaccine Clinical Trials (Sept 2007). The incidence of shift from baseline to worst post-baseline value will be summarized for on-treatment and on-study periods. Post-baseline lab results are defined as any assessment taken after the first dose no matter central lab or local lab data. If a patient is missing a baseline value but has a post-baseline value, then the baseline assessment will be labeled as “unknown”. Likewise, if a patient has a baseline value but has no post-baseline values, then the worst value will be labeled as “unknown”.

- Hemoglobin: shift from baseline to minimum post-baseline value
- WBCs: shift from baseline to minimum post-baseline value
- Platelets: shift from baseline to minimum post-baseline value
- BUN: shift from baseline to maximum post baseline value
- Creatinine: shift from baseline to maximum post-baseline value
- eGFR: shift from baseline to minimum post-baseline value
- Proteinuria: shift from baseline to worst post-baseline value
- ALT: shift from baseline to maximum post-baseline value
- AST: shift from baseline to maximum post-baseline value
- Alkaline phosphatase: shift from baseline to maximum post-baseline value
- Total bilirubin: shift from baseline to maximum post-baseline value

eGFR by will be graded using the following criteria:

- ≥ 90 mL/min/1.73m²
- ≥ 60 mL/min/1.73m² to < 90 mL/min/1.73m²
- ≥ 30 mL/min/1.73m² to < 60 mL/min/1.73m²
- ≥ 15 mL/min/1.73m² to < 30 mL/min/1.73m²
- < 15 mL/min/1.73m²

Shift tables for eGFR, ALT, AST and total bilirubin will be provided using confirmed values as well.

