The number and percent of patients who met a protocol-defined safety monitoring rule(s) and stopping rule(s) (see Protocol Section 8.6 for details) will be tabulated by treatment group. A listing

will be provided for patients who met protocol-defined safety monitoring rules and for patients who terminated treatment due to a protocol-defined stopping rule as well.

Additional investigation of hepatobiliary laboratory assessments, platelet counts and renal parameters will be performed for on-treatment and on-study periods as below.

Hepatobiliary Laboratory abnormalities: The number and percent of patients falling in each of the following category will be tabulated by treatment group:

- The higher of ALT > 3 x upper limit of normality (ULN) or ALT > 2 x baseline
- ALT/AST > 3 x ULN
- ALT/AST > 5 x ULN
- ALT/AST > 8 x ULN
- ALT > 3 x ULN - ≤ 5 x ULN
- ALT > 5 x ULN - ≤ 8 x ULN
- Total bilirubin > 2 x ULN
- ALP > 2 x ULN and (baseline ALP < 2 x ULN or baseline ALP missing)

The number and percent of patients falling in each of the following categories based on confirmed worst post-baseline assessments will be tabulated by treatment group and for pooled ISIS 703802.

- ALT/AST > 8 x ULN, which is confirmed
- ALT/AST > 5 x ULN, which is confirmed and persist for at least 2 weeks
- ALT/AST > 3 x ULN (or the greater of 2 x Baseline value or 3 x ULN if the Baseline value was > ULN), which is confirmed and either:
 - Total bilirubin > 2 x ULN, or
 - INR > 1.5, or
 - Temporal association with symptoms of fatigue, nausea, vomiting, right upper quadrant pain or tenderness (coded as abdominal pain or abdominal pain upper),, fever, rash or eosinophilia as a reported laboratory result > ULN; and where temporal will be defined as the report date of the confirmed laboratory parameter occurring within the interval of the associated adverse event start and stop dates.

For patients having confirmed 3-fold or greater elevations above the ULN for ALT or AST, a listing of all the ALT, AST, total bilirubin, INR, and alkaline phosphatase records will be provided.

Abnormalities of platelet counts: The number and percentage of patients falling in each of the following categories (using available central and local laboratory assessments) based on post-baseline assessments will be provided:

- Any 2 occurrences of platelet count < 140,000/mm³
- Any single occurrence of platelet count < 100,000/mm³

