- Any 2 occurrences of platelet count < 140,000/mm³ and any single occurrence of platelet count < 100,000/mm³

The nadir platelet count will be summarized by below categories:

- Decrease \geq 30% of baseline
- Decrease \geq 50% of baseline
- 100,000/mm³ to < 140,000/mm³
- 75,000/mm³ to < 100,000/mm³
- 50,000/mm³ to < 75,000/mm³
- 25,000/mm³ to < 50,000/mm³
- 0 to < 25,000/mm³

All categories of abnormalities in platelet count will be provided using confirmed values for on-study period as well.

Abnormalities of renal function: The number and percentage of patients falling in each of the following categories based on confirmed worst post-baseline assessments will be provided:

- eGFR by CKD-EPI > 25% decrease from baseline
- eGFR (CKD-EPI) value < 45 mL/min/1.73 m²
- urine albumin/creatinine ratio (UACR) > 165 mg/g (0.165 mg/mg)
- urine protein/creatinine ratio (UPCR) > 325 mg/g
- New onset hematuria defined as \geq 5 RBC/hpf (except for menstruating females)

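### Minor: the SAP's UACR and UPCR abnormality rows do not separate patients already above the cut-off at entry, and its eGFR >25% row uses a different baseline from the stopping rule with the same threshold

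*SAP*

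**What the plan says.** **Renal table (SAP 3.5.2).** The heading reads "Abnormalities of renal function: The number and percentage of patients falling in each of the following categories based on confirmed worst post-baseline assessments". There are five rows: eGFR decrease above 25%, eGFR below 45, "urine albumin/creatinine ratio (UACR) > 165 mg/g (0.165 mg/mg"), UPCR above 325 mg/g, and a row that opens "New onset hematuria defined as" at least 5 red cells per field. The UACR and UPCR rows say nothing about baseline. In the liver list of the same section, the ALP row does: "ALP > 2 x ULN and (baseline ALP < 2 x ULN or baseline ALP missing").

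**Confirmation and shift tables (SAP 3.5.2).** "If there is no retest within 7 days then the initial value is presumed confirmed". The shift list includes "Proteinuria: shift from baseline to worst post-baseline value" but does not name UACR.

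**Entry (Protocol 5.2).** UPCR of 0.25 mg/mg or more excludes, but "In the event of a UPCR above this threshold, eligibility may be confirmed by a quantitative total urine protein measurement of" less than 300 mg in 24 hours. eGFR below 60 excludes ("as determined by the Chronic Kidney Disease-Epidemiological Collaboration (CKD-EPI) Equation"). No numeric UACR limit is given.

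**Stopping rule (Protocol 8.6.2).** It lists the same five criteria, with UACR and UPCR also as absolute values. It applies only when nothing else explains the result.

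**Baselines.** Protocol 10.4, followed by SAP 3.2.6 and Table 2, takes the last value before first dose for measurements such as eGFR. Protocol 8.6 averages the Day 1 pre-dose value and the last earlier one for stopping rules. SAP 3.2.6 uses that average for ALT and AST, but not for eGFR.

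**The concern.** A table of post-baseline renal abnormalities is read as a table of things that happened on treatment. Every patient here has type 2 diabetes, so some may have albuminuria at entry. If such a patient stays above 165 mg/g, the UACR row counts the unchanged entry value. The other three renal rows cannot be met that way: one is a change from baseline, one is protected by the eGFR entry limit, and one is restricted to new onset. Confirmation does not filter these patients, because a stable high value confirms itself and an untested one is presumed confirmed.

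The eGFR row raises a different question. It carries the stopping rule's threshold but measures the fall from another starting value, so it can name different patients from those who met the rule.

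At stake is how the renal safety tables read. Groups have about 24 patients, so one patient is 1/24 = 4.2%. Kidney findings are followed closely for this drug: Protocol 6.2 makes any renal stopping-rule event an adverse event of special interest.

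**Working it through.** The plan states no figure on this point, so there is none to reproduce.

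**1. Can a patient enter above the cut-offs?** Inputs: Protocol 5.2 (UPCR 250 mg/g; override at 24-hour protein below 300 mg) and the SAP cut-offs. UACR divided by UPCR is the albumin share of urine protein.

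- UACR above 165 needs an albumin share above 165/250 = 66% at the UPCR limit. With the override it needs 165/300 = 55% at UPCR 300, or 165/375 = 44% at UPCR 375.
- UPCR above 325 needs the override. If the spot and 24-hour samples agree, creatinine excretion must be below 300/325 = 0.92 g/day.

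Both routes exist; the UPCR route is narrower. Investigator discretion (exclusions 9 and 30) may close either one for some patients.

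**2. How many patients?** The documents do not give the share of entrants above 165 mg/g. Assume a share p, that all of them stay above, and independent Binomial(24, p) counts in each of the four groups, with no drug effect.

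| p (assumed) | Expected of 96 | One given active group exceeds placebo by 2 or more | Any of three does |
|---|---|---|---|
| 1% | 1.0 | 2% | 6% |
| 2% | 1.9 | 5% | 15% |
| 5% | 4.8 | 15% | 34% |
| 8% | 7.7 | 21% | 42% |

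**3. eGFR limits, illustrative values.** The row's limit is 0.75 × Day 1. The rule's limit is 0.75 × (prior + Day 1)/2.

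- Prior 90, Day 1 80: row 60, rule 63.75. A confirmed 62 meets the rule and is not in the row.
- Prior 80, Day 1 90: row 67.5, rule 63.75. A confirmed 65 is in the row and does not meet the rule.

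**4. How often do the two disagree?** Assume a true eGFR of 85, independent normal errors with SD s on the prior, Day 1 and one post-baseline value, and a true fall f.

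- The mean distance to the limit is 85 × (0.25 − f) for both.
- The SD of that distance is s × √(1 + 0.75²) = 1.25s for the row and s × √(1 + 2 × 0.375²) = 1.132s for the rule.
- The covariance is s² × (1 + 0.75 × 0.375) = 1.281s², so the correlation is 1.281/(1.25 × 1.132) = 0.906.

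At f = 20% and s = 5 the mean distance is 4.25. The row flags Φ(−4.25/6.25) = 24.8% and the rule Φ(−4.25/5.66) = 22.6%. At f = 30% the figures are 75.2% and 77.4%. The average therefore does slightly better on both sides of a true 25% fall. At f = 25% disagreement is arccos(0.906)/π = 14% for any s.

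| True fall | Disagreement, s = 3 | s = 5 | s = 8 |
|---|---|---|---|
| 0% | 0.0% | 0.0% | 1.3% |
| 10% | 0.0% | 1.5% | 5.9% |
| 20% or 30% | 7.0% | 10.9% | 12.7% |
| 25% | 14% | 14% | 14% |

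Over falls of 0, 10, 15, 20, 25, 30 and 35%, the largest gap in total rates is 2.4 points (35% fall, s = 8: rule 82.6%, row 80.2%). The mismatch is mainly about which patients are counted. These figures treat a single post-baseline value, not the worst of several.

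**The case against.** The other side has a good case, and much of it stands.

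- **The urine rows match the protocol.** Protocol 8.6.2 also uses absolute UACR and UPCR limits. Restricting the rows to new exceedances would break that match, and would drop a patient who worsens sharply from a high baseline. This stands, and is why the rows should be kept.
- **Absolute rows are normal.** The SAP's QT rows and its bilirubin >2 × ULN row are also unconditioned. A patient with Gilbert's syndrome may enter at up to 3 mg/dL, which is above 2 × ULN if the laboratory's ULN is below 1.5 mg/dL. The heading promises worst post-baseline values, not treatment-emergent ones. This also stands: the rows are not an error.
- **Baseline context is planned.** There are by-visit change summaries, listings and a proteinuria shift table. A reader could separate the patients by hand, but the count itself does not.
- **Two baselines serve two purposes.** The SAP follows Protocol 10.4, and the stopping-rule table cites Protocol 8.6, which opens with the averaged definition. So the SAP does not contradict the protocol.

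A reader might infer three stronger things that the documents do not support. One is that the counts favour an arm; randomisation balances entry albuminuria in expectation. Another is that a patient who enters above 165 mg/g must be stopped. Protocol 8.6.2 exempts explained results, and 8.5.2 has the decision weigh all relevant data. The third is that aligning the eGFR baseline would make the two tables agree fully. The SAP row has no exemption for explained results, and the SAP presumes confirmation where Protocol 8.5 asks for a new specimen.

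**Conclusion.** Both observations hold, at minor weight: worth considering in descriptive safety tables, with no test, alpha or sample size involved.

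The UACR count, and less readily the UPCR count, can mix pre-existing with new exceedance. The size depends on an entry share that the documents do not give. At an assumed 1% the effect is about one patient in 96. At 5%, a chance excess of two or more over placebo in at least one active group has probability 34%. Both figures assume that every such patient stays above the cut-off.

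The eGFR row can flag different patients from the stopping rule, mostly when the true fall is near 25%. The 7-14% range rests on assumed within-person SDs of 3 to 8, a true eGFR of 85 and one post-baseline value.

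**What to change.** Change SAP 3.5.2 only.

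1. Keep the UACR and UPCR rows as they are, so that they still match Protocol 8.6.2. Under each, add two lines: baseline at or below the cut-off or missing, and baseline above the cut-off.
2. Add a UACR shift table beside the proteinuria one. Worsening from a high baseline then stays visible.
3. State that the eGFR >25% row uses the Protocol 8.6 average, as for ALT and AST. The stopping-rule table needs no change.

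If the SAP can no longer be amended, give the split as a supplementary table in the study report.

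The cost is a baseline flag, a few table lines, one shift table and one sentence. UACR and UPCR are already collected at Screening under Extended Urinalysis (Protocol Appendix A), and the stopping rule already needs both eGFR values. The downside is an eGFR baseline in this row that differs from the general definition in Protocol 10.4, which a footnote can state. Mismatches from the exemption for explained results and from the presumed-confirmed rule remain.

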3.5.3 Vital Signs Measurements

Vital signs will include blood pressure (SBP, DBP), body weight, body temperature, heart rate (HR), and respiratory rate (RR). Vital signs will be summarized using the descriptive statistics (n, mean, standard error, standard deviation, median, 25th percentile, 75th percentile, minimum, and maximum, mean 95% CI) for observed values, change from baseline, and percent change from baseline at each nominal study visit. Scheduled visit will be used for summary table.

3.5.4 12-Lead Electrocardiogram

ECGs will be performed in triplicate at the visits indicated in the protocol Schedule of Procedures. The ECG data will include ventricular rate, PR interval, QRS duration, QT and corrected QT intervals, and overall interpretation. For the continuous variables, the average of measurements at a given visit will be used for analysis. For the continuous variables above, descriptive statistics (n, mean, standard error, standard deviation, median, 25th percentile, 75th percentile, minimum, maximum, and mean 95% CI) of the results, as well as the change from baseline to each study visit, will be presented by treatment group in summary tables. Scheduled visit will be used for summary table.

The number and percent of patients who have the following reported events will be tabulated by treatment group and for pooled ISIS 703802.

- Absolute QT/QTcF/QTcB >450 msec
- Absolute QT/QTcF/QTcB >480 msec
- Absolute QT/QTcF/QTcB >500 msec
- Increase from baseline in QT/QTcF/QTcB >30 msec
- Increase from baseline in QT/QTcF/QTcB >60 msec
- Increase from baseline in PR \geq 50% (if absolute baseline <200 msec)
- Increase from baseline in PR \geq 25% (if absolute baseline >200 msec)
- Increase from baseline in QRS \geq 50% (if absolute baseline <100 msec)
- Increase from baseline in QRS \geq 25% (if absolute baseline >100 msec)

QTcB (msec) = QT (msec) / (RR)^{1/2}; if RR is missing, use QT (msec) * (HR(bpm)/60)^{1/2}

QTcF (msec) = QT (msec) / (RR)^{1/3}; if RR is missing, use QT (msec) * (HR(bpm)/60)^{1/3}

All the data collected in triplicate will be listed.

3.6 *Interim Analysis*

There is no interim analysis planned for the study.

5 APPENDICES

Appendix A – Efficacy Measurement Analysis Visit Window

Lipids: Total Cholesterol (TC) , LDL cholesterol (LDL-C) , HDL cholesterol (HDL-C) , Non-HDL cholesterol (non-HDL-C), Triglycerides (TG), VLDL cholesterol (VLDL-C) , Lp(a), FFA, ApoB-48, ApoB-100, ApoB, ApoC-III, Apo A-I.

PD parameters: ANGPTL3, fasting insulin, HOMA-IR, Proinsulin, C-peptide, Fructosamine, Glycated albumin, Delipidated Free Glycerol, Fasting Plasma Glucose.

Phospholipids (if available): Ceramides, Sphingolipids, Diacylglycerol

| Study Week | Target Day for Cohort A | Study Day Window for Cohort A | Target Day for Cohort B/C | Study Day Window for Cohort B/C |
|---------------------|-------------------------|-------------------------------|---------------------------|---------------------------------|
| Screening | -35 to -8 | ≤ -8 | -35 to -8 | ≤ -8 |
| Qualification Visit | -7 to -1 | -7 to < 1 | -7 to -1 | -7 to < 1 |
| 1 | 1 | 1 | 1 | 1 |
| 5 | 29 | 2 to 43 | 29 | 2 to 43 |
| 9 | 57 | 44 to 71 | 57 | 44 to 71 |
| 13 | 85 | 72 to 99 | 85 | 72 to 99 |
| 17 | 113 | 100 to 127 | 113 | 100 to 127 |
| 21 | 141 | 128 to 155 | 141 | 128 to 155 |
| 25 | NA | NA | 169 | 156 to 183 |
| 26 | 176 | 156 to 179 | NA | NA |
| 27 | 183 | 180 to 197 | NA | NA |
| Follow up week 4 | 211 | 198 to 225 | 197 | 184 to 211 |
| Follow up week 8 | 239 | 226 to 256 | 225 | 212 to 242 |
| Follow up week 13 | 274 | >256 | 260 | >242 |

HbA1c, leptin, and adiponectin

| Period week | Target Day for Cohort A | Study Day Window for Cohort A | Target Day for Cohort B/C | Study Day Window for Cohort B/C |
|-------------------|-------------------------|-------------------------------|---------------------------|---------------------------------|
| Screening | -35 to -8 | < 1 | -35 to -8 | < 1 |
| 1 | 1 | 1 | 1 | 1 |
| 13 | 85 | 55 to 115 | 85 | 55 to 115 |
| 25 | NA | NA | 169 | 139 to 199 |
| 27 | 183 | 153 to 213 for Cohort A | NA | NA |
| Follow up week 13 | | >213 | | >199 |

Hepatic fat fraction (HFF), SAT volume, VAT volume, SAT area, VAT area, VAT volume/SAT Volume ratio by MRI

| Period week | Target Day for Cohort A | Study Day Window for Cohort A | Target Day for Cohort B/C | Study Day Window for Cohort B/C |
|-------------|-------------------------|-------------------------------|---------------------------|---------------------------------|
| Baseline | -12 to -1 | <= 1 | -12 to -1 | <= 1 |
| 13 | 85 | 55 to 115 | 85 | 55 to 115 |
| 25 | NA | NA | 169 | 139 to 199 |
| 27 | 183 | 153 to 213 | NA | NA |

Record selection rules to identify analysis visit for use in efficacy analysis and summary tables is as follows:

Priority order for lipids, PD parameters, phospholipids and HbA1c is 1) Fasting records, 2) Nearest target day, 3) If equal distance (in days), choose the earlier one. 4) If on the same day, average of records

Priority order for other test is 1) Nearest target day, 2) If equal distance (in days), choose the earlier one. 3) If on the same day, average of records.

Appendix B – Repeated Measures Efficacy Visit Mapping Instructions for Sensitivity Analysis 6 and Model

For the MMRM analysis of Triglycerides we will be mapping per Appendix A for assignment to the analysis visits. For the MMRM we should only include the following analysis visit timepoints in the model: Week 5, 9, 13, 17, 21, PAT.

For the QW weekly treatment schedule include baseline, analysis visits week 5, 9, 13, 17, 21 and 27 where data in analysis visit 27 is mapped to a common visit to be used in both dosing schema, suggest week 100.

For Q4W treatment schedule include baseline, analysis visits week 5, 9, 13, 17, 21 and 25 where data in analysis visit 25 is mapped to a common visit to be used in both dosing schema, suggest week 100.

The sample SAS code for the repeated measures analysis can be found below:

```
*****  
* Note: Base = baseline *  
* Y= post-baseline value at primary analysis time point  
* TRTP = Treatment group: pooled placebo, 40 mg Q4W, 80 mg Q4W, 20 mg QW  
*****  
ods output lsmeans=lsme diffs=diff;  
proc mixed data = dataset;  
  class TRTP (ref='pooled placebo') avisit patient;  
  model log(Y/base) = TRTP log(BASE) AVISIT AVISIT*TRTP  
  repeated AVISIT / subject=patient (TRTP) type=un  
run;
```

Appendix C – Below the Level of Quantification Instructions

When observing (due to urine albumin (<0.30 mg/dL) or urine protein (<4 mg/dL) levels falling below the detection limit) a result of “Cannot calc” for urine albumin/creatinine ratio (UACR) or urine protein/creatinine ratio (UPCR) in the central laboratory data from Medpace, derive the UACR and UPCR assuming the worst case for urine albumin and urine protein (hence the highest values). This would mean setting the below detection albumin and protein results to the detection limit by dropping the ‘<’ sign and dividing by urine creatinine.

For example: In the LAB data, LABTYPE = ‘Urinalysis’:

If LABTEST = ‘P/C Ratio (Urine Protein/Urine Creatinine)’ and RESULTC=‘Cannot calc’, set ‘Protein, quantitative’ to 4 and compute UPCR (mg/mg) as “Protein, quantitative (mg/dL) divided by Urine Creatinine (mg/dL)”.

If LABTEST = ‘Albumin/Creatinine Ratio’ and RESULTC=‘Cannot calc’, set ‘Urine Albumin’ to 0.3 and compute UACR (mg/g) as “1000 x Urine Albumin (mg/dL) divided by Urine Creatinine (mg/dL)”.

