Missing WBC differential absolute counts and percentages will be derived: If WBC differential absolute counts are missing, and percentages are available, then absolute counts will be calculated by multiplying the percentage by total WBC count. Conversely, if absolute count is available, and percentage is missing, then percentage will be calculated by dividing absolute count by the total WBC count. If neutrophil counts and percentages are missing, and segmented neutrophil and band neutrophil results are available, then neutrophils will be calculated by adding segmented neutrophils and band neutrophils.

Quantitative laboratory measurements reported as '< X', i.e. below the lower limit of quantification (BLQ), or '> X', i.e. above the upper limit of quantification (ULQ), i.e. outside the limit of quantification, will be converted to X (or limit of quantification) for the purpose of quantitative summaries. If urine albumin/creatinine ratio (UACR) or urine protein/creatinine ratio (UPCR) is 'Cannot calc' indicating urine albumin or urine protein in the below quantification range, UACR and UPCR will be calculated as the ratio of urine albumin or urine protein to urine creatinine after converting urine albumin or urine protein to the limit of quantification. See Appendix C for details.

Estimated Glomerular Filtration Rate (eGFR) is based on the Chronic Kidney Disease-Epidemiological Collaboration (CKD-EPI) Equation and is provided as a parameter in the central laboratory.

All laboratory test results will be listed. Separate listings will be provided for local and central labs. A separate listing for platelets will be provided that includes assessment from both local and central labs.

Chemistry, hematology, coagulation, other assessments and quantitative urinalysis (observed value, and change and percent change from baseline) will be summarized using descriptive statistics (n, mean, standard error, standard deviation, median, 25th percentile, 75th percentile, minimum, and maximum, mean 95% CI) by nominal study visit. Urinalysis dipstick protein will be summarized using frequency counts by nominal study visit. Lab summary table except for platelet count will be based on the scheduled visits in central lab data only with the results in original unit. Two sets of

summary tables will be provided for platelets. One is based on central lab data, the other is based on local lab data. Note baseline platelets uses both central and local in its calculation.

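### A urine protein result below detection can be tabulated as a confirmed UPCR above 325 mg/g when the urine is very dilute

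*SAP*

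**What the plan says.** SAP 3.5.2 (Laboratory Measurements) says that results outside the quantification range "will be converted to X (or limit of quantification) for the purpose of quantitative summaries". The next sentence covers ratios the laboratory returned as 'Cannot calc': "UACR and UPCR will be calculated as the ratio of urine albumin or urine protein to urine creatinine", after the numerator has been moved to its limit. That sentence does not repeat the restriction to quantitative summaries.

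Appendix C gives the detail. The trigger is albumin below 0.30 mg/dL or "urine protein (<4 mg/dL) levels falling below the detection limit". The instruction is to "derive the UACR and UPCR assuming the worst case for urine albumin and urine protein (hence the highest values", and it continues: "This would mean setting the below detection albumin and protein results to the detection limit". UPCR is computed in mg/mg and UACR in mg/g.

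The renal abnormality table in SAP 3.5.2 gives patient counts in "categories based on confirmed worst post-baseline assessments will be provided". One row is "urine protein/creatinine ratio (UPCR) > 325 mg/g". On confirmation, the same section states: "If there is no retest within 7 days then the initial value is presumed confirmed". A better value within 7 days leaves the initial value unconfirmed. The table text does not mention derived ratios.

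**The concern.** Substituting the limit is a reasonable convention for a mean or median. It behaves differently in a table of threshold crossings. With the numerator fixed at 4 mg/dL, the ratio no longer carries information about protein and reflects only how concentrated the urine is. In a dilute enough sample it crosses 325 mg/g, although the laboratory measured no quantifiable protein and reported no ratio.

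Renal function is one of the organ systems for which the protocol sets specific monitoring and stopping rules (Protocol 8.5.2 and 8.6.2), so this row will be read closely. Each treatment group has about 24 patients, and one patient moves the row by 1/24 = 4.2 percentage points. The word 'confirmed' in the table would also suggest a repeat test that may never have been done.

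**Working it through.** The documents state no figure on this point, so there is none to reproduce. The check has three parts.

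**1. When a derived ratio crosses the threshold.** Inputs: protein limit 4 mg/dL and albumin limit 0.30 mg/dL (Appendix C); thresholds UPCR 325 mg/g = 0.325 mg/mg and UACR 165 mg/g (SAP 3.5.2).

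- Derived UPCR (mg/g) = 1000 × 4 / creatinine (mg/dL). It exceeds 325 when creatinine < 4/0.325 = 12.3 mg/dL.
- Derived UACR (mg/g) = 1000 × 0.3 / creatinine (mg/dL). It exceeds 165 when creatinine < 300/165 = 1.8 mg/dL.

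| Urine creatinine (mg/dL) | Derived UPCR (mg/g) | Above 325? | Derived UACR (mg/g) | Above 165? |
|---|---|---|---|---|
| 5 | 800 | yes | 60 | no |
| 8 | 500 | yes | 37.5 | no |
| 10 | 400 | yes | 30 | no |
| 12 | 333 | yes | 25 | no |
| 12.4 | 323 | no | 24 | no |
| 20 | 200 | no | 15 | no |
| 50 | 80 | no | 6 | no |
| 100 | 40 | no | 3 | no |

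The true UPCR lies below the derived value. If the derived value is 325 or less, the true value is certainly not above 325. If it is more than 325, the true value may be on either side. At creatinine 10 mg/dL, for example, a true protein of 3.5 mg/dL gives 350 mg/g and a true protein of 1 mg/dL gives 100 mg/g. Both are reported as below 4 mg/dL and both are derived as 400 mg/g.

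**2. Whether such a value would count as confirmed.** Protocol 6.2 schedules renal samples every 14 days ± 2 days for three months and monthly afterwards. Two neighbouring samples in the dense period are at least 14 − 2 − 2 = 10 days apart, so the schedule supplies no retest within 7 days. The Protocol 8.5.2 alert, which leads to a repeat test, needs a UPCR above 325 mg/g. A 'Cannot calc' result gives no number to compare, so I infer that it raises no alert. By default the derived value is then presumed confirmed.

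**3. How many patients (illustration only).** The documents give no distribution of urine creatinine. Protocol Appendix A implies about 13 post-baseline urines per patient in Cohort A and 12 in Cohorts B and C. Let p be the assumed share of samples with both creatinine below 12.3 mg/dL and protein below detection, independent between samples. The chance of at least one is 1 − (1 − p)^n.

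| Assumed p | n = 12 | n = 13 | Patients out of 96 |
|---|---|---|---|
| 0.1% | 1.2% | 1.3% | about 1 |
| 0.5% | 5.8% | 6.3% | about 6 |
| 1% | 11.4% | 12.3% | about 11 |

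If dilute samples cluster within patients, fewer patients are affected at the same p.

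**The case against.** The best defence is the wording in SAP 3.5.2 that limits the conversion to quantitative summaries. The ratio sentence follows in the same paragraph, so the substitution could be read as serving descriptive statistics only. That reading is possible, but no text applies it to the ratios or keeps derived values out of the abnormality table. A programmer could go either way.

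The rule is also pre-specified, openly conservative and identical in all groups. That stands: it does not by itself favour any group. The SAP offers cross-checks too, since all laboratory results are listed, dipstick protein and proteinuria shifts are tabulated, and UACR has its own row. These would help a reader question an isolated UPCR count, but they do not correct it.

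Protocol 6.2 asks for a redraw when a test is uninterpretable or missing. If a site treated 'Cannot calc' in that way, a better value within 7 days would undo the confirmation. The examples given there are clumping, hemolysis and insufficient quantity, so a below-detection result is not clearly covered.

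A reader might infer that every such case is a false exceedance. The documents do not support that: the protein is censored, not zero, and the true ratio can exceed 325. A reader might also infer that derived ratios inflate the count of patients meeting a stopping rule, or could stop dosing. Protocol 8.5 requires confirmation on new specimens, and 8.6.2 requires that there be no alternative explanation. A derived ratio with no retest does not meet those terms, and nothing says that it affects dosing. The point concerns the separate renal abnormality table.

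**Conclusion.** The concern holds for that table. As written, the SAP allows a censored, indeterminate result to be reported as a confirmed UPCR above 325 mg/g whenever urine creatinine is below 12.3 mg/dL. The threshold arithmetic is exact. The route into the table rests on two readings: that the restriction to quantitative summaries does not cover the categorical table, and that a 'Cannot calc' result prompts no retest within 7 days.

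The size in patients cannot be determined from the documents. The counts of about 1, 6 or 11 out of 96 follow from assumed rates and should not be taken as estimates. UACR is affected only below 1.8 mg/dL creatinine, so this is in practice a UPCR issue. Counts could rise in any group, with no built-in direction between groups.

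**What to change.** Amend SAP 3.5.2 and Appendix C as follows.

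- Keep derived ratios in the descriptive summaries, flagged as upper bounds.
- In the UPCR > 325 mg/g and UACR > 165 mg/g rows, class a derived ratio at or below the threshold as not exceeding.
- Report a derived ratio above the threshold in a separate row, indeterminate (numerator below detection). Do not count it as a confirmed exceedance, and do not apply presumed confirmation to it.
- Flag these records in the listings.
- State that UPCR is converted from mg/mg to mg/g before the cut-off is applied. The renal table gives the mg/mg equivalent for UACR but not for UPCR.

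Classing all derived ratios as not exceeding would be wrong in the other direction, because an upper bound above 325 does not show that the value is below it. A smaller substitute only moves the problem: half the limit lowers the creatinine cut-off to 2/0.325 = 6.2 mg/dL, and the limit divided by √2 lowers it to 8.7 mg/dL.

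The cost is a few lines of SAP text and one derivation flag, with no new data. The downside is one extra table row.
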